### **Title of study**

Impact of two prednisone-free maintenance immunosuppressive regimens with reduced dose FK506+Everolimus vs. standard dose FK506+MMF on subpopulation of T and B cells, renal allograft function and gene expression profiles in renal allograft biopsies at 12, 24 and 36 months post-transplant. Prospective single center study in recipients of renal transplant allograft.

### **Study purpose and rationale**

Immunosuppressive therapy with the calcineurin inhibitors (CNI) cyclosporine (CsA) and tacrolimus (Tac), has radically changed the field of organ transplantation. Ironically, although extensively and effectively used for kidney and other solid organ transplants, CsA and Tac cause significant adverse renal side effects: acute and chronic renal dysfunction, hemolytic-uremic syndrome, hypertension, electrolyte disturbances and tubular acidosis. Chronic nephrotoxicity from CNI has been implicated as a principal cause of post-transplant renal dysfunction. It is characterized by an irreversible and progressive tubular atrophy, interstitial fibrosis, and focal hyalinosis of small renal arteries and arterioles. Furthermore, by blocking IL2 production, this class of medications is also associated with a negative impact on generation of regulatory T cells, or (Tregs). (Tregs are an important subpopulation of helper T cells that has been associated with positive immunomodulation and donor specific hypo-responsiveness).

In renal transplant recipients, complete avoidance of calcineurin inhibitors from the time of renal transplant surgery has been associated with increased incidence of acute cellular rejection. The combination of mTOR inhibitors with full dose CNI has been shown to be synergistically nephrotoxic, and has been associated with poor graft outcome. We and other investigators have tested conversion from CNI to mTOR inhibitors with promising results. We have shown that in a prednisone-free immunosuppression regimen, conversion from tacrolimus to mTor inhibitors is safe, and not associated with an increased risk of acute rejection. More importantly, we have shown that it is associated with a persistent increase of regulatory T cells (Data presented at ATC 09 and 2010).

Recently, the A2309 study led to FDA-approval of Everolimus. The A2309 was a study designed to combine reduced dose CsA+Everolimus. Interestingly, the reduced exposure to CsA was not associated with an increased rate of ACR; renal allograft function was well maintained when compared to that of the control group. This study

---

study leads us to question the mechanism(s) behind the efficacy of a low dose CNI with an mTOR inhibitor in preventing acute allograft rejection.

The present proposal is designed to investigate the mechanisms of the synergistic effect(s) of low dose CNI and mTOR inhibitors (Everolimus) in controlling alloreactive T and B cells while expanding Tregs.

Our hypothesis, based on published data and our laboratory results (see preliminary data-Supportive documents), is that mTOR inhibitors allow expansion of Tregs and that low exposure to CNI is sufficient to control alloreactive T cells. Decreased exposure to CNI and concomitant increase of Tregs will then translate to improved renal allograft function and histology.

### **Objectives**

The overall aim of the present study is to prospectively investigate the impact of two maintenance immunosuppressive regimens (both prednisone-free) on subpopulations of T and B cells and on renal allograft function at 12, 24 and 36 months post-randomization. One regimen combines low CNI exposure (tacrolimus) with concentration controlled Everolimus, and the second combines standard dose CNI (Tacrolimus) with MMF.

The primary endpoints of the study are to: 1) evaluate the impact of the two maintenance immunosuppressive regimens on T cells subpopulations, including regulatory T cells and B cell subpopulations, at different time points post renal transplant, and 2) determine the impact of the two regimens on renal allograft function at 12, 24 and 36 months post-randomization (post-transplant). Secondary endpoints of the study are to: 1) evaluate the impact of the two regimens on allograft immunohistopathology gene expression profiles and graft infiltrating cells (memory T cell (CD4+ or CD8+ CD45RO+), TREG (CD4+FoxP3+), memory B cell (CD19+CD27+)) at 12 and 24 months in renal allograft biopsies, and 2) evaluate the impact of the regimens on acute rejection, graft loss and death at 12, 24 and 36 months post-transplant.

### **Population**

The study will be conducted at Northwestern University Feinberg School of Medicine/Northwestern Memorial Hospital, and subjects will be recruited during visits to the Comprehensive Transplant Center. We plan to enroll and randomize recipients and their respective donors until 40 recipients have started the study drug to which they were randomized. As of January 2014, 3 recipients randomized to the experimental arm and 1 randomized to the control arm were withdrawn prior to dosing due to surgical complications. Replacement pairs will be enrolled, bringing the prospective enrollment to a minimum of 44 donor/recipient pairs (at least 88 total subjects).

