**Study design**

**Renal Transplant Recipients:**

All recipients will receive the same induction immunotherapy at time of transplant. : Campath (30mg IV x1) will be administered at the time of surgery. Methylprednisolone (500 mg IV) will be administered on the day of transplant and on days 1 (250 mg IV), and 2 (125 mg IV) post-transplant. No further steroids will be given post-transplant unless indicated by the following medical conditions: acute renal allograft rejection, renal diseases necessitating the use of steroids, and other systemic diseases such as rheumatoid arthritis (RA), systemic lupus erythematosus (SLE), and asthma.

Maintenance immunosuppression is administered according to the 1:1 randomization at time of enrollment: 20 subjects will begin **standard dose tacrolimus and MMF (control arm)**

Tacrolimus will be initiated according to our practice. The dose will be adjusted from day 3 on to achieve a target whole blood trough concentration of 8 ng/mL to 10 ng/mL. From month 2 until Month 6, the target tacrolimus trough level will be reduced to 6 ng/mL to 8 ng/mL. After month 6, the target level will be reduced to 4 ng/mL to 8 ng/mL.

MMF dose will be initiated as 1 g b.i.d. (2 g/day). Adjustments should be made for adverse events including but not limited to gastrointestinal intolerance and a decrease in WBC. MMF trough or AUC shall not be used to adjust dosing.

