**Twenty (20) subjects will begin low dose tacrolimus with concentration controlled everolimus (treatment arm)**

Tacrolimus will be initiated according to our practice. In this treatment arm, the Tacrolimus dose will be adjusted from day 3 on, to a target whole blood trough concentration of 4 ng/mL to 7 ng/mL. From month 2 until Month 6, the target Tacrolimus trough level will be 3 ng/mL to 6 ng/mL. After month 6, the Tacrolimus dose should be adjusted in order to achieve a target trough level of 2 ng/mL to 5 ng/mL.

From day 5 on, the starting dose of Everolimus (0.75 mg bid) will be increased if the trough level is < 3 ng/mL, or reduced if the trough level is > 8 ng/mL.

All drugs will be administered in an open label fashion.

The following transplant recipient data will be collected at the time of randomization:.  
Demographics: Age at transplantation, sex and race.

Causes of end-stage renal disease

Transplant related information: donor age, histocompatibility and cross match data, viral serology, history of acute rejection and delayed graft function, use of ACEI and/or ARB, level of renal allograft function - estimated GFR ( e-GFR(12) using MDRD formula, proteinuria.

Blood samples will be obtained prior to randomization from all renal transplant recipients for baseline T and B cell functional activity and characterization of the cell subpopulations by flow cytometry.

-All recipients will be routinely followed at our Transplant center with post-transplant labs (SMA7, CBC, and relevant immunosuppression trough levels).

Additional blood will be collected and analyzed for the study at 3, 6, 12, 24 and 36 months post-randomization. If the final blood sample cannot be drawn at the 36 month timepoint, it may be drawn up to 50 months post-transplant. These samples will be used to investigate the impact of the two maintenance immunosuppressive regimens on subpopulation of T cells in comparison with baseline levels. Specifically,

---

we will look at regulatory T cells (Treg: Foxp3+CD4+ CD25bright+) that could have been generated via the two maintenance immunonousuppressive regimens, and correlate the generation of with their function.

RNA from peripheral blood will be also collected and stored for post-hoc analyses of T and B-cell immunoresponse gene expression via gene arrays.

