**Donors:**

Blood samples from donor subjects will also be obtained at either the time of randomization or post-surgery during standard-of-care follow-up appointments. These donor leukocytes will be used as stimulator cells in studies of functional activity of recipient T-cells. These samples will be processed in the principal investigator's research laboratory.

---

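### Open-label randomisation at enrolment, apparently before surgery, with replacement of non-starters, lets a decision made after the arm is known define the 40 recipients who count

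*Combined protocol and SAP*

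**What the plan says.** On timing, the Study design section (Renal Transplant Recipients) states: "Maintenance immunosuppression is administered according to the 1:1 randomization at time of enrollment". The treatment-arm text adds: "All drugs will be administered in an open label fashion".

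On who counts, the Population section sets the stopping point for enrolment: "We plan to enroll and randomize recipients and their respective donors until 40 recipients have started the study drug to which they were randomized". It then reports, as of January 2014, that "3 recipients randomized to the experimental arm and 1 randomized to the control arm were withdrawn prior to dosing due to surgical complications", and continues: "Replacement pairs will be enrolled, bringing the prospective enrollment to a minimum of 44 donor/recipient pairs (at least 88 total subjects".

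No sentence says outright that randomisation precedes surgery. Two places imply it. The withdrawals above were of recipients already randomised, for surgical reasons, before any dose. The Donors section lets donor blood be drawn "at either the time of randomization or post-surgery during standard-of-care follow-up appointments", which sets the two times against each other. One place fits poorly: the data to be collected at randomisation include "history of acute rejection and delayed graft function", together with estimated GFR of the allograft and proteinuria. The Objectives section also treats time since randomisation and time since transplant as the same clock.

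The Statistical analysis section names no analysis set. It does not say whether withdrawn recipients are followed or analysed. No section defines which surgical complications lead to withdrawal, or who decides.

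**The concern.** Randomisation makes the arms comparable as assigned. If surgery comes after assignment, and a recipient with a complication can be withdrawn and replaced by someone who knows the arm, the group of starters rests partly on that judgement. Complicated surgery plausibly goes with worse early graft function. Graft function is a primary endpoint, and rejection, graft loss and death are secondary. If such recipients were withdrawn more readily from the everolimus arm, the starters would flatter everolimus, which is the direction of the trial's hypothesis. The planned covariate adjustment covers baseline differences only, and a complication of surgery is not a baseline characteristic when assignment comes first.

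The plan gives no reason to assign so early. Induction is the same for everyone, and tacrolimus is started by local practice in both arms. The arms first differ at the tacrolimus target from day 3 and at the first MMF or everolimus dose.

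**Working it through.** **1. The plan's own figures.** Population section: 40 starters + 3 + 1 withdrawn = 44 pairs, and 44 × 2 = 88 subjects. This reproduces exactly. Sample size section: 20 per arm with 10% attrition leaves 18. A two-sided t-test at 0.05 then has power 0.83 at an effect size of 1.0 and above 0.999 at 2.0, against the stated 0.82 and 0.99. Replacement keeps 40 starters, so power is not the issue here; comparability is.

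**2. When randomisation happens.** Randomised recipients lost to surgical complications before dosing, and a contrast between randomisation and post-surgery for donors, point to assignment before surgery. Delayed graft function and allograft function cannot be observed before the transplant, so the list of data collected at randomisation points the other way. The first reading is better supported, because it rests on what happened to four recipients, but the sections need reconciling.

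**3. Is the split evidence of arm-dependent removal?** The documents do not give the numbers randomised per arm. Assume 20 starters in each arm, so 23 everolimus and 21 control were randomised.

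- Everolimus: 3/23 = 13.0%. Control: 1/21 = 4.8%.
- Fisher exact, two-sided: p = 0.61. With equal arms of 10, 15 or 22 instead, p = 0.58, 0.60 or 0.61.
- Exact binomial, 3 of 4 against one half: p = 0.625; 95% interval for the everolimus share 19% to 99%.

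Four events say almost nothing about differential removal.

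**4. How large could the effect be?** Let k be the deficit in graft function, in SD, of the removed recipients. The documents give no value, so k is an assumption. Relative to an analysis of everyone randomised, dropping them moves the arm difference towards everolimus by

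shift = k × (3/23 − 1/21) = k × 0.083.

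| Assumed k (SD) | Shift (SD) | Two-sided rejection rate with no true effect, 20 per arm |
|---|---|---|
| 0.5 | 0.04 | 5.2% |
| 1.0 | 0.08 | 5.8% |
| 1.5 | 0.12 | 6.7% |

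The shift is a bias in the comparison of starters only if comparable complicated recipients were kept in the control arm. The arms are treated alike until after surgery, so complications themselves should not depend on arm. If one threshold for withdrawal applied to both, the starters in each arm are uncomplicated cases alike and the expected bias is 0, whatever the observed split. The range is therefore 0 to about 0.12 SD for k up to 1.5. Further withdrawals before dosing would change it, and 44 pairs is stated only as a minimum.

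**The case against.** The strongest case against has four parts.

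First, a reader might infer from 3 v 1 that complicated recipients are already being removed selectively from the everolimus arm. The documents do not support that. The split is well within chance, no denominators are given, and no section says who decided or on what grounds. With a common threshold the expected bias is zero. This stands, and it is why the point concerns an open route to bias rather than an observed bias.

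Second, the effect is small next to the effect size of 1.0 that the trial is sized to detect for graft function, in what the protocol calls a pilot. This also stands and limits the weight of the point.

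Third, a reader might conclude that no later analysis can repair the damage. That goes too far. Graft function, rejection, graft loss and death can be compared in everyone randomised, dosed or not, and the protocol says recipients are followed routinely at the centre with post-transplant laboratory tests. An all-randomised analysis could repair part of the problem for those outcomes. The plan does not provide for one, though it does not rule one out either. It would also dilute the comparison of regimens, because undosed recipients contribute no exposure.

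Fourth, moving randomisation needs a post-operative window whose length the documents do not give. The first MMF and everolimus doses are undated; everolimus adjustment begins on day 5, so its first dose is earlier. The number of pairs still to be randomised is not given either. Both are fair limits. The four withdrawals show that some interval between surgery and dosing exists, and the change can be confined to future pairs.

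**Conclusion.** The concern holds in limited form. Under the plan as written, enrolment continues "until 40 recipients have started the study drug to which they were randomized", and a decision that can be made with the arm known determines who is among them. Assignment before surgery is a sound inference, not a stated fact, and one list in the protocol fits it poorly. Nor do the documents state that the person deciding knew the arm; open-label treatment with assignment at enrolment leaves that possible.

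Four withdrawals (3 everolimus, 1 control) have occurred. They show that removal after randomisation happens, not that it depends on arm. The possible shift in graft function is 0 to about 0.12 SD towards everolimus. It rests on 20 starters per arm and an assumed deficit of up to 1.5 SD in those removed. Stated power is unaffected. The change is worth making because it is cheap and closes the route, not because the present data show harm.

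**What to change.** **For pairs not yet randomised**, amend the Study design section so that consent and baseline blood come before transplant. Randomisation then follows surgery, once the recipient is confirmed able to start either regimen and before any arm-specific treatment or tacrolimus target. State that window explicitly, since the first MMF and everolimus doses are not dated. Pairs lost before that point still have to be made up to reach 40 starters, but as screen failures decided without knowledge of the arm.

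**For recipients already randomised**, keep all of them, including the four withdrawn, in their assigned arms. Follow them for graft function, rejection, graft loss and death where data exist, and report the withdrawals by arm with reasons. Add an all-randomised analysis of those outcomes to the Statistical analysis section.

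**For consistency**, state when randomisation occurs relative to surgery, and reconcile the list of data collected at randomisation with it.

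The cost is a short amendment, an assignment step in the early post-operative days, some follow-up of withdrawn recipients, and two randomisation timings within one small trial. If few pairs remain, moving randomisation gains little, but the follow-up, reporting and all-randomised analysis still apply.

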### **Inclusion Criteria:**

---

- 1) Adults between 18 and 70 years of age
- 2) Either gender and of any ethnic background
- 3) Single-organ recipients (kidney only)
- 4) Able to understand the protocol and provide informed consent.
- 5) Recipient of living donor kidney transplants
- 6) PRA<20%

**Exclusion criteria:**

- 1) End Stage Renal Disease (ESRD) secondary to primary FSGS (focal segmental glomerulonephritis).
- 2) Inability to fully understand the purpose of the study and the inability to sign the informed consent
- 3) A significant or active infection
- 4) Pregnant or nursing females
- 5) History of severe hyperlipidemia not controlled with statins, subjects with Cholesterol > 400mg/dl
- 6) Platelet count <100,000mm3, WBC < 2,000mm3 (or clinical practice)
- 7) Any surgical, medical or psychiatric condition, other than the current transplant, which in the opinion of the investigator precludes enrollment into this trial

**Number of centers & subjects**

Northwestern University Feinberg School of Medicine /Northwestern Memorial Hospital.

**Investigational and reference therapy**

Everolimus. Dose: 0.75mg PO BID (concentration controlled).

**Study duration**

We expect the total duration for this study not to exceed 2 years from the date of the last subject's enrollment.

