Kidney biopsy samples will be collected with standard-of-care samples at time of transplant (back table), 3 months, 12 months and at 24 months post-transplant. These will help evaluateand compare the impacts of the two maintenance immunonousuppressive regimens on allograft immunohistopathology. Gene expression profiles will also be analyzed. These samples will be processed in the principal investigator's research laboratory.

Both groups of subjects will be followed through 36-months post-randomization. In addition to monitoring renal allograft function, we will evaluate the incidence of acute rejection, subject and graft survival, incidence of hypertension (HTN), malignancies, opportunistic infections and post-transplant diabetes mellitus (DM).

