**Statistical analysis:**

The primary endpoints of the study are graft function and subpopulations of T cells, including regulatory T cells and B cell subpopulations at 3, 6, 12, 24 and 36 months post kidney transplant. The secondary endpoints of the study include 1) incidence of acute rejection, graft loss, and death at 12, 24 and 36 months post kidney transplant; 2) allograft immunohistopathology and gene expression profiles at 12 and 24 months post kidney transplant.

We will run univariate and bivariate analyses for all variables prior to our main analyses. We will evaluate continuous variables using t-tests or F-tests and categorical variables using  $\chi^2$ . We will examine data distributions and test all variables for linear relationships or non-linear relationships.

Descriptive statistics (means, standard deviation, frequency) and correlations (both Pearson and Spearman) among variables will be calculated for preliminary data assessment.

Necessary transformation and imputations will be carried out based on the raw data distribution.

As missing data are inevitable in a longitudinal study, we will determine whether missing data are MCAR (data are missing completely at random), MAR (data are missing at random), or NMAR (not missing at random). If missing data are MCAR or MAR, it is likely that the standard multivariate computations using PROC MI (multiple imputations) will not result in biased standard error estimates. However, if missing data are NMAR, we will use the "pattern mixture" approach to compute a weighted average of the parameters that are associated with the missing data to estimate what the data would have been.

For the primary objective, we hypothesize that subjects receiving low dose CNI with mTOR inhibitor (Everolimus) will exhibit significantly greater graft function and higher numbers of regulatory T cells as compared to the standard dose CNI+MMF group.

We will utilize both repeated-measures ANOVA and random mixed effect models to compare the trajectory change in graft function and proportion of regulatory T cells over 12, 24 and 36 months between the two experimental groups. The method of estimation will be maximum likelihood (ML).

---

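### The stated study duration (at most 2 years after the last enrolment) is 12 months too short for the planned 36-month assessments

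*Combined protocol and SAP*

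**What the plan says.** All references are to the combined protocol and SAP.

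- **Study duration:** "We expect the total duration for this study not to exceed 2 years from the date of the last" subject's enrolment. No other overall duration appears in the readable text. The figure in the evaluation schedule is not reproduced there.
- **Objectives, primary:** "determine the impact of the two regimens on renal allograft function at 12, 24 and 36 months post-randomization (post-transplant"). The Statistical analysis section lists months 3, 6, 12, 24 and 36 for both graft function and the cell subpopulations.
- **Objectives, secondary:** "evaluate the impact of the regimens on acute rejection, graft loss and death at 12, 24 and 36 months post-transplant". Histology and gene expression stop at month 24.
- **Study design, time origin:** "Maintenance immunosuppression is administered according to the 1:1 randomization at time of enrollment".
- **Study design, follow-up:** "Both groups of subjects will be followed through 36-months post-randomization".
- **Study design, late sample:** "If the final blood sample cannot be drawn at the 36 month timepoint, it may be drawn up to 50 months post-transplant".
- **Statistical analysis:** the models are to "compare the trajectory change in graft function and proportion of regulatory T cells over 12, 24 and 36 months between the two experimental groups".

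**The concern.** A study that ends no later than 24 months after its last enrolment cannot contain a month-36 visit for the last recipient. Month 36 is not a peripheral visit. It is the final time point of both primary endpoints, the last point of the planned trajectory comparison, and a reporting time for rejection, graft loss and death.

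The overall duration is the figure a reader would use to decide when the study may close. If it were followed, the most recently enrolled recipients, including any late replacement pairs described under Population, would have no month-36 assessment. No section says that month-36 results are limited to earlier enrollees, and none defines administrative censoring.

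**Working it through.** **1. The gap**

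Inputs: ceiling of 24 months from the last enrolment (Study duration); randomization at enrolment, follow-up to month 36, and optional final draw up to month 50 (Study design).

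- Last recipient's final assessment = enrolment + 36 months. Shortfall = 36 − 24 = **12 months**. The follow-up schedule does not reproduce the stated 24 months.
- If the late blood draw is used to its limit, 50 − 24 = 26 months, taking transplant as close to enrolment. This concerns one blood sample only.

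**2. Can another clock close the gap?**

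- Randomization is at enrolment, so counting from randomization gives the same 36 months. A later transplant date would widen the gap for visits counted from transplant.
- Donors do not supply a later starting date. The Population section says "We plan to enroll and randomize recipients and their respective donors until 40 recipients have started the study drug", so each donor is enrolled with the recipient.

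**3. Who would be affected if the study closed at 24 months**

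A recipient enrolled *t* months before the last one has *t* + 24 months of follow-up at closure. Month 36 is reached only if *t* ≥ 12. With uniform accrual over *A* months (both assumed; the documents give no accrual period), the share lacking month 36 is 12/*A*, or all recipients if *A* ≤ 12.

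| Assumed accrual *A* (months) | Share without month 36 | Of 40 recipients |
|---|---|---|
| 48 | 12/48 = 25% | 10 |
| 36 | 12/36 = 33% | about 13 |
| 24 | 12/24 = 50% | 20 |
| 18 | 12/18 = 67% | about 27 |
| 12 or less | essentially 100% | essentially 40 |

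**4. Illustrative cost in precision at month 36**

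Assume a likelihood analysis with known covariance, a separate mean per visit, and only month 36 missing, in a share *f* of recipients. Relative to full follow-up, the standard error of the month-36 difference is

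ratio = √[(1 − R²)/(1 − f) + R²],

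where R² is the squared multiple correlation of month 36 with the four earlier visits. Within-subject correlation ρ is assumed to lie between 0.5 and 0.9.

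- Autoregressive, ρ = 0.5 per 12 months: R² = 0.5² = 0.25. At *f* = 0.50, √(0.75/0.50 + 0.25) = √1.75 = 1.32.
- Compound symmetry, ρ = 0.9: R² = 4ρ²/(1 + 3ρ) = 3.24/3.7 = 0.876. At *f* = 0.50, √(0.124/0.50 + 0.876) = √1.124 = 1.06.

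These two cases bound the range over both structures: 1.02–1.12 at *A* = 48, 1.03–1.17 at 36, 1.06–1.32 at 24 and 1.12–1.58 at 18. At *A* ≤ 12 the month-36 comparison essentially cannot be made. Repeated-measures ANOVA, which is also planned, would lose more if it were run on complete cases.

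**5. Is the power statement affected?**

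Sample size and power gives 0.82 and 0.99 for effect sizes 1.0 and 2.0, with 10% attrition at 12 months. With 20 × 0.9 = 18 per arm, a two-sided t-test at 0.05 has noncentrality 1.0 × √(18/2) = 3 on 34 degrees of freedom. Its power is 0.83 for effect size 1.0 and above 0.999 for 2.0. That agrees closely with the stated figures. The calculation claims nothing specific to month 36, so the duration error does not alter it.

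**The case against.** The strongest reply is that the sentence is only a forecast. It is worded as an expectation, whereas the 36-month follow-up is worded as something that will be done. The objectives, blood schedule, follow-up statement and analysis all point to month 36, and one sentence is out of line. The natural inference is a duration that does not match the schedule, not a plan to stop early. This stands, and it keeps the point minor. It does not remove it: a forecast that cannot be met under the protocol's own schedule still has to be corrected.

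Stronger readings that a reader might infer, and that the documents do not support:

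- *The plan cuts follow-up at 24 months.* It does not. Follow-up through month 36 is stated directly, so any loss depends on closing by the duration sentence.
- *The duration is 26 months short.* That figure applies only to an optional late blood draw. Graft function, rejection, graft loss and death have no such extension, so the required shortfall is 12 months.
- *Only a quarter to a half of recipients are at risk.* This follows from assuming 24 to 48 months of accrual and is not a bound. Faster accrual makes the share larger, and late replacement pairs make uniform accrual doubtful.
- *The results would be biased or the power claim fails.* A calendar cut-off is plausibly unrelated to outcome, so the cost would be mainly precision under the longer accruals, and loss of the month-36 comparison under the shortest. The power statement makes no month-36 claim.

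**Conclusion.** The concern holds as a minor internal inconsistency. The only overall duration in the readable text is 12 months too short for the follow-up, the primary endpoints and the rejection, graft-loss and death outcomes that the same document plans at month 36. That figure rests on the text alone.

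The consequence is conditional. Month-36 data would be missing only if the study closed on the stated timeline, and only for recipients enrolled less than 12 months before the last one. The shares and standard-error ratios above are illustrations. They depend on an accrual length, uniform entry and correlations that the documents do not give. Months 3 to 24 and the biopsies fall within the 24 months and are unaffected.

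**What to change.** Reconcile the sections by amending the Study duration sentence to at least 36 months after the last recipient's randomization or transplant, with allowance for the final blood draw up to month 50 post-transplant where it is used. The cost is one sentence, submitted to the IRB as a protocol amendment. No visit, sample or analysis is added, because the 36-month follow-up is already planned.

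If closure 24 months after the last enrolment is really intended, that is a larger change. The protocol would have to say that month-36 results cover earlier enrollees only, with administrative censoring, and the analysis and reporting of month 36 would change accordingly.
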